3.5 Early Study Termination

The study can be terminated at any time for any reason by the Sponsor (including approval or the favourable opinion is revoked, in the event of a negative change in the benefit/risk ratio when the necessary adjustment to the maximum sum insured is not possible; failure to enrol; futility; safety decision etc). If the trial is suspended or terminated early, the Investigator will promptly inform the trial patients and should assure appropriate therapy and follow-up.

No further IMP will be given to a patient if any study permanent discontinuation rules are met (see Section 9.1), including recommendation of the Independent Data Monitoring Committee (IDMC; Section 3.8). If a patient withdraws from the study treatment early but consent is retained, study assessments may be continued until a) Day 169 (Week 24) for patients who withdraw from study treatment during the first study period and therefore are **not** eligible for

Version number: 1

1-Mar-2022

LTE, or b) until Day 365 (Week 52) or the end of the safety follow-up period in patients who withdraw from study treatment after Day 169 (Week 24).

Unless patients continue in the LTE at Day 169 (Week 24) or due to loss of clinical response at or after Day 197 (Week 28), a safety follow-up for 140 days after the last dose of IMP will be required.

In addition, the Investigator may withhold further IMP from a patient if they report moderate-or-severe (regardless of seriousness) adverse reactions which are attributed to the IMP. There will be no obligation to unblind treatment allocation in making this decision.

The Sponsor may discontinue the entire study at any time based on information received during the running of the study that demonstrates an unexpected risk or absence of benefit to patients. This may for example follow the request of the IDMC or where additional information emerges either during the study or from other sources (eg, literature or Health Authorities).

If the study is discontinued, where patients withdraw early or where IMP has been discontinued by the Investigator, patients will be required to be followed-up for a minimum of 140 days for safety evaluation.

Further details of IMP discontinuation are provided in Section 9.1.

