8.1.3 Adverse Events of Special Interest

Adverse events of special interest, defined below, will be reported to Sponsor or designee within 24 hours of learning of the event:

- Systemic or localised allergic reactions that require immediate treatment*.
- Severe injection site reactions that last longer than 24 hours.
- Any severe or opportunistic viral, bacterial or fungal infection and/or any uncommon, unanticipated or persistent infection (viral, parasitic, bacterial, or fungal).
- Any malignancy.
- Increase in alanine transaminase (ALT) $>3 \times$ upper limit of normal (ULN); see the "Increase in ALT" flow chart in Section 17.12 (Appendix 12).

The special situations of:

- Symptomatic overdose (serious or non-serious) with IMP (any administration that is twice or more than the intended dose administered in less than 3 weeks [21 days]).
- Pregnancy discussed separately in Section 8.3.

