9.1 Discontinuation of the Patient from Investigational Medicinal Product

9.1.1 Reasons for Permanent Discontinuation of Investigational Medicinal Product

The IMP will be permanently discontinued for any of the following reasons:

- 1. Anaphylactic reaction or other severe systemic reaction to the IMP injection.
- 2. Diagnosis of a malignancy during the study.
- 3. Major surgery.
- 4. Severe intercurrent illness.
- 5. Evidence of confirmed pregnancy.

6. Any infection that is opportunistic, such as active TB, non-tuberculous mycobacterial infections and other infections whose nature or course may suggest an immunocompromised status.

1-Mar-2022

Version number: 1

- 7. Severe laboratory abnormalities:
 - Absolute neutrophil count $\leq 0.5 \times 10^9 / L$;
 - Platelet count $\leq 50 \times 10^9 / L$;
 - Serum ALT >3 ULN and Total Bilirubin >2 ULN;
 - Serum ALT >5 ULN if baseline ALT ≤2 ULN or ALT >8 ULN if baseline ALT >2 ULN.

Note: If the laboratory abnormality is considered causally related to the IMP, the IMP will be permanently discontinued. In cases where a causal relationship to the IMP can be reasonably excluded (ie, an alternative cause is evident), the IMP will be discontinued but it may be resumed when the laboratory abnormality is sufficiently normalised.

8. If a subject experiences an adverse event assessed as ≥ Grade 3 CTCAE [severe; see Section 8.1.1.1] (or ≥ Grade 2 CTCAE [moderate; see Section 8.1.1.1] for the System Organ Classes of Cardiac disorders and Blood and Lymphatic disorders) per CTCAE v5.0, the subject should be discontinued from further dosing. Such subjects should not be discontinued from the study, but they should be monitored by their medical practitioner and study investigator until the adverse event (AE) resolves or stabilizes.

Other reasons that may lead to the permanent discontinuation of IMP include:

- Treatment with any prohibited systemic concomitant medication or procedure (see Section 5.3.2 and Section 5.3.4).
- Treatment with any topical concomitant rescue therapy in the first 14 days from Baseline (see Section 5.3.4).
- After Day 14, treatment with topical concomitant rescue therapy on more than
 2 occasions during study participation. The maximum permitted duration of topical
 concomitant rescue therapy on either occasion is 2 consecutive weeks. If duration of
 treatment is exceeded on either occasion this will also lead to permanent
 discontinuation of IMP.

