9.1.2 Reasons for Temporary Discontinuation of Investigational Medicinal Product

Dosing of IMP should be temporarily interrupted for the following reasons:

- 1. Clinically important laboratory abnormalities, such as:
 - Absolute neutrophil count $\leq 1.0 \times 10^9 / L$ but $> 0.5 \times 10^9 / L$;
 - Platelet count $\leq 100 \times 10^9 / L$ but $> 50 \times 10^9 / L$;
 - Creatine phosphokinase $>10 \times ULN$.
- 2. Other intercurrent illness.
- 3. An infection requiring systemic treatment with antibiotic, antifungal, antiviral, antiparasitic or antiprotozoal agents, or requiring oral treatment with such agents for more than 2 weeks.

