9.1.2.1 Re-challenge

Reinitiation of intervention with the IMP will be done under close and appropriate clinical and/or laboratory monitoring once the Investigator will have considered according to his/her best medical judgment that the responsibility of the IMP(s) in the occurrence of the concerned adverse event was unlikely and if the selection criteria for the study are still met (refer to Section 4).

If there is to be a delay to any dosing of IMP outside of the permitted visit windows as per the Schedule of Assessments (Section 6.1), the Investigator must consult with, and receive written confirmation that dosing can be rescheduled from, the Medical Monitor.

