9.1.2.1.1 Study intervention restart or rechallenge after liver stopping criteria met

Study intervention restart or rechallenge after liver chemistry stopping criteria are met by any participant in this study is not allowed.

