9.1.3 Follow-up of Patients Off Treatment

If a patient discontinues study treatment prematurely, she/he will be encouraged to remain in the study to complete all remaining study visits and to participate in all assessments according to the Schedule of Assessments. Their study data collected during their continued involvement is important to the study efficacy analysis and study value.

If a patient permanently withdraws from study treatment early but consent is retained, study assessments may be continued until Day 169 (Week 24) for patients who withdraw from study treatment in the first study period (and who are therefore no longer eligible for consideration for the LTE at Day 169 (Week 24) or progression to the next study period), or until Day 365 (Week 52) in patients who withdraw from study treatment after Day 169 (Week 24) and who decide not to participate in or are **not** eligible for the LTE study. This may be followed by the safety follow-up according to the Schedule of Assessments (Section 6.1).

If a patient chooses not to attend remaining visits in the event of withdrawal from study treatment early before Day 169 (Week 24) or Day 365 (Week 52), they will instead enter the safety follow-up and complete their assessments as per the Schedule of Assessments (Section 6.1).

Patients will be considered lost to follow-up only if no contact has been established by the time the study is completed, such that there is insufficient information to determine the patient's status at that time. Patients who refuse to continue participation in the study, including telephone contact, should be documented as "withdrawal of consent" rather than "lost to follow-up." Investigators should document attempts to re-establish contact with missing patients throughout the study period. If contact with a missing patient is re-established, the patient should not be considered lost to follow-up, and evaluations should resume according to the protocol.

The following actions must be taken if a patient fails to return to the clinic for a required study visit:

• The site must attempt to contact the patient and reschedule the missed visit as soon as possible and counsel the patient on the importance of maintaining the assigned visit schedule.

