17.12 Appendix 12 - Liver safety: suggested actions and follow-up assessments

INCREASE IN ALT

In ANY CASE, FOLLOW the instructions listed in the box below:

- 1. INFORM the Site Monitor who will forward the information to the Study Manager
- 2. INVESTIGATE specifically for malaise with or without loss of consciousness, dizziness, and/or hypotension and/or episode of arrhythmia in the previous 72 hours; rule out muscular injury
- 3. PERFORM the following tests:
 - LFTs: AST, ALT, alkaline phosphatase, total and conjugated bilirubin and prothrombin time / INR
 - CPK, serum creatinine, complete blood count
 - Anti-HAV IgM, anti-HBC IgM (HBV-DNA if clinically indicated), anti-HCV and HCV RNA, anti-
 - CMV IgM and anti-HEV IgM antibodies
 - Depending on the clinical context, check for recent infection with EBV, herpes viruses, and toxoplasma
 - Hepatobiliary ultrasonography (or other imaging investigations if needed)
- 4. CONSIDER Auto-antibodies: antinuclear, anti-DNA, anti-smooth muscle, anti-LKM
- 5. CONSIDER consulting with hepatologist
- CONSIDER patient hospitalisation if INR>2 (or PT<50%) and/or central nervous system disburbances suggesting hepatic encephalopathy
- 7. MONITOR LFTs after discontinuation of IMP:
 - As closely as possible (or every 48 hours) until stabilization, then every 2 weeks until return to normal/baseline or clinical resolution.
- **8. FREEZE** serum sample (5ml x 2)
- 9. In case of SUSPICION of GILBERT Syndrome, a DNA diagnostic test should be done

"Baseline" refers to ALT sampled at the Baseline Visit; or if the Baseline value unavailable, to the latest ALT sampled before the Baseline Visit. The algorithm does not apply to the instances of increase in ALT during screening.

See Section 17.10 (Appendix 10) for guidance on safety reporting.

Normalisation is defined as \leq ULN or baseline value, if the Baseline value is > ULN.

^{*}If unable to retest in 72 hours, use original lab results to decide on further reporting/monitoring/discontinuation. Note:

17.14 Appendix 14 - Contingency Measures for a Regional or National Emergency That is Declared by a Governmental Agency

1-Mar-2022

Version number: 1

Contingency procedures are suggested for an emergency that prevents access to the study site, to ensure the safety of the patients, to consider continuity of the clinical study conduct, protect trial integrity, and assist in maintaining compliance with GCP in Conduct of Clinical Trials Guidance.

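### The Note under Protocol 9.1.1 item 7 lets IMP resume after a liver stopping criterion when another cause is evident; Section 9.1.2.1.1 forbids any such restart

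*Protocol*

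**What the plan says.** Section 9.1.1 gives the reasons for stopping IMP permanently. Item 7 has four laboratory criteria: a neutrophil count, a platelet count, ALT >3 ULN with total bilirubin >2 ULN, and ALT >5 ULN (or >8 ULN if baseline ALT exceeds 2 ULN). The Note below them splits by cause. An abnormality attributed to IMP is a permanent stop. If IMP can reasonably be excluded as the cause, "the IMP will be discontinued but it may be resumed when the laboratory abnormality is sufficiently normalised". The Note speaks of the laboratory abnormality in general and so covers all four criteria.

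Section 9.1.2.1, on re-challenge, lets the Investigator restart IMP after judging that "the responsibility of the IMP(s) in the occurrence of the concerned adverse event was unlikely", provided the selection criteria are still met. Its subsection 9.1.2.1.1 then states: "Study intervention restart or rechallenge after liver chemistry stopping criteria are met by any participant in this study is not allowed". It makes no exception for cause.

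Section 3.5 adds: "No further IMP will be given to a patient if any study permanent discontinuation rules are met", and refers to Section 9.1 for those rules.

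**The concern.** A patient who meets an item 7 liver criterion, has a clear other cause and then normalises may be re-dosed under the Note and may not be re-dosed under 9.1.2.1.1. Neither section refers to the other.

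The inconsistency matters because it can err in the unsafe direction. A site that never restarts complies with both rules, since the Note only permits resumption. A site that relies on the Note can breach 9.1.2.1.1.

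It can also lead to unequal handling. Under Section 9.1.3, a patient who permanently withdraws from treatment in the first period is "no longer eligible for consideration for the LTE at Day 169 (Week 24) or progression to the next study period". Two sites with the same kind of patient could therefore reach different outcomes for re-dosing, for the LTE at Week 24 and for entry to the second period.

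**Working it through.** There is no plan figure to reproduce. The check sets the texts side by side and follows one patient through them.

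**Step 1: which criteria are involved.** Item 7 has 4 criteria, of which 2 are liver criteria: 2/4 = 50%. This counts criteria, not patients.

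**Step 2: what 9.1.2.1.1 refers to.** The visible text does not define liver chemistry stopping criteria under that name. Section 9.1.2, item 1, introduces its list with "Clinically important laboratory abnormalities, such as" and names neutrophils, platelets and CPK: 0 of 3 are liver tests. The two ALT criteria in item 7 are the only liver thresholds for stopping IMP in the visible text, so they are the natural referent.

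**Step 3: one patient, both rules.** Take baseline ALT ≤2 ULN, on-study ALT >5 ULN, an evident other cause, and ALT later normal.

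| Rule | Applies to this patient? | Result |
|---|---|---|
| 9.1.1 item 7 Note | Yes: item 7 criterion met, IMP excluded as cause, value normalised | IMP may resume |
| 9.1.2.1.1 | Yes: liver stopping criterion met, any participant | IMP may not restart |

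**Step 4: can the two be reconciled by cause?** One could try reading the ban as covering drug-related cases and the Note as covering the rest. The structure does not allow that. Section 9.1.2.1.1 sits under 9.1.2.1, which already confines restart to cases where IMP responsibility was judged unlikely. Drug-related cases are excluded before the subsection is reached, so the ban can only act on other-cause cases. Those are the cases the Note permits.

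**Step 5: would another control catch it?**
- Section 8.1.3 makes ALT >3 ULN an event that "will be reported to Sponsor or designee within 24 hours of learning of the event". Every item 7 liver case has ALT above 3 ULN (thresholds 3, 5 and 8), so all should be reported. But 8.1.3 does not say which restart rule applies.
- Section 9.1.2.1 requires the Medical Monitor's written confirmation only when dosing is delayed beyond the visit window.
- Dosing is every 28 days. Appendix 12 asks for liver tests "As closely as possible (or every 48 hours) until stabilization, then every 2 weeks until return to normal/baseline or clinical resolution". If values stabilise within 28 − 14 = 14 days of the stop, at least one two-weekly check falls within a 28-day interval, and the earlier 48-hourly checks can also show recovery. Normalisation can therefore be documented before the next scheduled dose, so that no delay arises and no written confirmation is needed. This shows that it can happen, not how often.

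**The case against.** The strongest reply is that the protocol can be read safely as it stands. The Note is permissive and general. Section 9.1.2.1.1 is mandatory, liver-specific, has its own heading and covers every participant, so a specific prohibition should limit a general permission. Section 3.5 supports this reading. This stands as evidence of intent. It does not remove the contrary permission: the Note is attached directly to the liver thresholds, and Section 3.5 sends the reader to Section 9.1, where the Note itself sits.

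A second reply concerns safeguards. Besides 24-hour reporting, Appendix 12 requires the site in every case to tell the Site Monitor, who informs the Study Manager. Section 9.1.2.1 requires close monitoring and continued eligibility. An unnoticed re-dose would need several misses. This is fair, and it limits the likely harm, but none of these steps tells the site which rule to apply.

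Two stronger readings are tempting and not supported:
- A reader might infer that the protocol nowhere resolves the conflict. That cannot be said with confidence. The Appendix 12 ALT flow chart is not shown, and a surviving footnote indicates that it deals with discontinuation. Section 5.2.7 (Dose Modification) appears in the table of contents, but its body is not visible. Either could define the stopping criteria or state a restart rule.
- A reader might infer that item 8 (stopping for higher-grade adverse events) also needs a sentence giving it precedence over the Note and the 9.1.2 pauses. No defect in item 8 has been shown. Because Section 8.1 allows an abnormal laboratory finding to be an adverse event, such a sentence could cancel the neutrophil and platelet restart that the Note rightly allows, and turn temporary pauses into permanent stops.

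**Conclusion.** The inconsistency holds. For the two liver criteria of item 7, the Note permits what 9.1.2.1.1 forbids, and no visible text limits the Note. The ban is probably the intended rule. The neutrophil and platelet criteria are not affected.

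This rests on two assumptions: that the stopping criteria named in 9.1.2.1.1 are the item 7 ALT thresholds, and that the unseen flow chart and Section 5.2.7 do not already limit the Note. If the unseen text set the liver stopping criteria higher than item 7, the overlap would be partial; if at or below those levels, it would be complete.

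The documents give no event rate, so no patient count is offered; few patients are likely to be affected. No sample size, power or other statistical figure changes. It is a drafting error in a safety instruction, worth correcting because the correction costs almost nothing.

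**What to change.** Limit the resumption sentence of the item 7 Note to the neutrophil and platelet criteria, and add: *For the liver criteria, IMP is permanently discontinued whatever the cause and may not be restarted (Section 9.1.2.1.1).* Check that the Appendix 12 flow chart and Section 5.2.7 say the same. Leave item 8 as it is.

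The cost is one sentence limited and one added at the next amendment, plus a letter to sites. No extra patients, visits or data fields are needed. The downside is that a patient whose ALT rise has a clear other cause cannot restart, which 9.1.2.1.1 already requires.

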9.1.2 Reasons for Temporary Discontinuation of Investigational Medicinal Product

Dosing of IMP should be temporarily interrupted for the following reasons:

- 1. Clinically important laboratory abnormalities, such as:
 - Absolute neutrophil count $\leq 1.0 \times 10^9 / L$ but $> 0.5 \times 10^9 / L$;
 - Platelet count $\leq 100 \times 10^9 / L$ but $> 50 \times 10^9 / L$;
 - Creatine phosphokinase $>10 \times ULN$.
- 2. Other intercurrent illness.
- 3. An infection requiring systemic treatment with antibiotic, antifungal, antiviral, antiparasitic or antiprotozoal agents, or requiring oral treatment with such agents for more than 2 weeks.

9.1.2.1 Re-challenge

Reinitiation of intervention with the IMP will be done under close and appropriate clinical and/or laboratory monitoring once the Investigator will have considered according to his/her best medical judgment that the responsibility of the IMP(s) in the occurrence of the concerned adverse event was unlikely and if the selection criteria for the study are still met (refer to Section 4).

If there is to be a delay to any dosing of IMP outside of the permitted visit windows as per the Schedule of Assessments (Section 6.1), the Investigator must consult with, and receive written confirmation that dosing can be rescheduled from, the Medical Monitor.

9.1.2.1.1 Study intervention restart or rechallenge after liver stopping criteria met

Study intervention restart or rechallenge after liver chemistry stopping criteria are met by any participant in this study is not allowed.

9.1.3 Follow-up of Patients Off Treatment

If a patient discontinues study treatment prematurely, she/he will be encouraged to remain in the study to complete all remaining study visits and to participate in all assessments according to the Schedule of Assessments. Their study data collected during their continued involvement is important to the study efficacy analysis and study value.

If a patient permanently withdraws from study treatment early but consent is retained, study assessments may be continued until Day 169 (Week 24) for patients who withdraw from study treatment in the first study period (and who are therefore no longer eligible for consideration for the LTE at Day 169 (Week 24) or progression to the next study period), or until Day 365 (Week 52) in patients who withdraw from study treatment after Day 169 (Week 24) and who decide not to participate in or are **not** eligible for the LTE study. This may be followed by the safety follow-up according to the Schedule of Assessments (Section 6.1).

If a patient chooses not to attend remaining visits in the event of withdrawal from study treatment early before Day 169 (Week 24) or Day 365 (Week 52), they will instead enter the safety follow-up and complete their assessments as per the Schedule of Assessments (Section 6.1).

Patients will be considered lost to follow-up only if no contact has been established by the time the study is completed, such that there is insufficient information to determine the patient's status at that time. Patients who refuse to continue participation in the study, including telephone contact, should be documented as "withdrawal of consent" rather than "lost to follow-up." Investigators should document attempts to re-establish contact with missing patients throughout the study period. If contact with a missing patient is re-established, the patient should not be considered lost to follow-up, and evaluations should resume according to the protocol.

The following actions must be taken if a patient fails to return to the clinic for a required study visit:

• The site must attempt to contact the patient and reschedule the missed visit as soon as possible and counsel the patient on the importance of maintaining the assigned visit schedule.

• Before a patient is deemed lost to follow-up, the Investigator or designee must make every effort to regain contact with the patient or next of kin by, for example, repeat telephone calls, certified letter to the patient's last known mailing address, or local equivalent methods. These contact attempts should be documented in the patient's medical record.

1-Mar-2022

Version number: 1

• Efforts to reach the patient should continue until the end of the study. Should the patient be unreachable at the end of the study, the patient should be considered to be lost to follow-up.

